# Pre-Assessment –

All women scheduled to undergo multicompartment native tissue vaginal repair with plan for same day surgical discharge will be screened for their eligibility. If eligible and consenting, the following baseline data will be collected on paper forms that will then be transcribed into a secure REDCap (Research Electronic Data Capture) Database:

- 1. Demographic data including age, race, BMI, zip code
- 2. Medical and Surgical History
- 3. Menopausal status, including current exposure to topical vaginal estrogen
- 4. Type of planned surgical procedure
- 5. Plan for concomitant sling placement
- 6. Assessment of post-void residual volume (collected via bladder scan or CIC)

# Randomization -

All enrolled and consented patients will undergo randomization at their pre-operative clinic visit. A study patient can be randomized into either tamsulosin IP or Placebo IP group. Randomization assignment will occur through sealedenvelope.com-generated random allocation using a randomly permutated block design (8 subjects per block). An

unblended designated person who will not participate in data collection or analysis will be responsible for providing randomization schedule. Study staff will dispense the assigned IP bottle (see below) in the urology clinic. Study patient charts will get updated with the IP ID (e.g. 01A, 02A, 01B, 02B...). Research staff administering follow-up questionnaires will also be blinded to the subject's randomization. The subject will be asked to bring back their IP bottle at the time of their postoperative visit.

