# Study Design

This is a double-blind, randomized controlled trial. Both investigators and participants will remain blinded to the intervention. All surgery will be performed by FPMRS board-certified urogynecologists. The patients will be able to have a revealing of the intervention they received at 6 weeks post-surgery

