#### Study Intervention –

10 pills of each IP and placebo will be placed in identical coded containers and stored in a locked area in the clinic. Instructions for IP usage will be provided to subjects for 10 days of usage as 0.4 mg qd by PO route starting 5 days prior to day of surgery and continued for a total 10 days. The research manager will be the only member of the study team who has the research key designating which containers are IP versus placebo.

On postoperative day 0 after recovery from anesthesia, each patient will have their bladder emptied using the indwelling Foley and their bladder will then be retrograde-filled with 300 cc of normal saline and given 30 minutes to void. A postvoid residual volume<150 cc will be considered a success of the voiding trial. If the voiding trial was considered failed, the patient will have a foley catheter reinserted and the patient will be instructed to remove the catheter at home after having a bowel movement. If they are unable to void at home within 4 hours of catheter removal, they will return to the Wake Forest Urology clinic for self-catheter teaching.

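### The study-product ID charted for each woman ends in an undefined letter that most naturally marks the arm; if it does, learning what one letter means reveals the arm of all 88 women

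*Combined protocol and SAP*

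**What the plan says.** The Randomization section describes two groups: "A study patient can be randomized into either tamsulosin IP or Placebo IP group". Allocation uses a "randomly permutated block design (8 subjects per block"), and no stratification factor or second site is named. Study staff dispense the assigned bottle in the clinic. The section then states: "Study patient charts will get updated with the IP ID (e.g. 01A, 02A, 01B, 02B", the list ending in an ellipsis. It does not say what the number or the letter stands for.

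The safeguards are in three places:

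- Study Design: "Both investigators and participants will remain blinded to the intervention".
- Randomization: "Research staff administering follow-up questionnaires will also be blinded to the subject's randomization".
- Study Intervention: "10 pills of each IP and placebo will be placed in identical coded containers", and "The research manager will be the only member of the study team who has the research key designating which containers are IP versus placebo".

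Two other statements bear on timing. Study Design allows each woman to be told, six weeks after surgery, which treatment she received. Project Schedule puts enrolment and data collection between March 2021 and April 2022.

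No section says who runs or scores the day-0 voiding trial, or whether that person sees the product ID.

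**The concern.** A bottle code should identify the bottle and nothing else. If the code has a part shared by everyone in the same arm, the blind depends on a single fact: which letter is active. Keeping the key with one person protects that fact, but it does not hide which women belong together. Once someone who sees the IDs learns one woman's treatment, the others follow without access to the key.

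The outcomes leave some room for expectation to act. The primary endpoint is a voiding trial run by staff, started once the patient has recovered from anesthesia, with a 30-minute limit and a residual-volume cutoff of 150 cc. Satisfaction with voiding is asked on a seven-point scale before discharge and at one week. The trial's case for a causal reading of both rests on its being double-blind.

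**Working it through.** **1. What the letter could mean.** The documents give no definition, so the readings have to be compared with what the plan describes.

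| Reading | For | Against |
|---|---|---|
| Arm | Two letters shown and two arms; numbers restart under each letter; no strata or sites for a letter to mark | Not stated; the list is only an example and is left open |
| Block | 88 / 8 = 11 blocks, so letters A to K with numbers restarting in each would fit | Not stated |
| Bottle batch | Possible for any coded container | No batches are described |

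Arm is the most natural reading. It remains an inference.

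**2. How many allocations one disclosure exposes.** Inputs: 88 women, 44 per group (Power analysis); blocks of 8 (Randomization).

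- Letter = arm: the decoded letter gives 44 women and the other letter gives the remaining 44. 44 + 44 = 88 of 88.
- Unique codes without arm information: 1 of 88. Even if block boundaries were known, another woman in the same block would be in the opposite arm with probability 4/7 = 57%, close to a coin toss.

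**3. Whether a disclosure can come while women are still being assessed.** The reveal is offered at six weeks after each woman's own surgery. It is not held back until the trial closes. Enrolment and data collection last about 13 to 14 months. Early participants therefore reach six weeks while later ones are still to be operated on. The protocol does not say who tells the woman or whether clinic staff hear the answer.

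**4. Whether the letters could be guessed without a reveal.** Suppose someone compared voiding-trial failures by letter. With X ~ Bin(n, p for placebo) and Y ~ Bin(n, p for tamsulosin), the chance that the placebo letter shows strictly more failures is P(X > Y):

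| Women per letter | 24.3% v 2.9% (Power analysis) | 24.6% v 8.7% (earlier randomised trial, Background) |
|---|---|---|
| 8 | 83% | 70% |
| 12 | 91% | 79% |
| 20 | 97% | 88% |

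This supports a guess and proves nothing to the person guessing. It assumes that the stated rates are true and that someone keeps such a tally.

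**5. Block size, as a side point.** If the letters are visible in sequence and the block size is known, the last assignments in a block become certain once one letter has been used four times. Of the 70 possible 4:4 blocks, 40 have one such assignment, 20 have two, 8 have three and 2 have four. The mean is (40×1 + 20×2 + 8×3 + 2×4) / 70 = 112 / 70 = 1.6 per block, or 11 × 1.6 = 17.6 of 88 (20%). What is predicted is a letter; it becomes a treatment only after decoding.

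**The case against.** The strongest reply is that the plan never says the letter is the arm. The IDs are an open-ended example, 11 block letters would fit as well arithmetically, and a key that designates which containers are active reads like a container-by-container list. If the letter is a block or batch, neither 88 of 88 nor 17.6 of 88 applies. This stands as a limit on certainty. It does not remove the point, because a two-letter arm code would also need a key and the reader has no means of ruling it out.

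Second, access is not documented. The text says study patient charts; the electronic record is named separately under Data Monitoring, and paper forms are kept in a locked research cabinet. A reader might infer that the surgical team, recovery staff and interviewers all see the letter. The documents do not say so, and they state that investigators and questionnaire staff are blinded. What stands against this is that nothing keeps the ID from those who assess outcomes, and that clinic staff hand out the coded bottles.

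Third, some decoding routes are weak. The listed drug effects, such as nausea, constipation, headache and dizziness, are common after surgery and would raise suspicion without identifying a letter. A bottle mix-up does not reveal contents, and no emergency unblinding procedure is described. The six-week reveal is the route that the plan itself provides.

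Fourth, a reader might infer that the double blind and allocation concealment are lost for the whole trial. That goes too far. The 88 counts exposed allocations, not biased results. Voiding trials already recorded cannot be changed by later knowledge, the procedure has a fixed fill, time limit and cutoff, and satisfaction is the woman's own rating, made before her reveal.

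**Conclusion.** The point holds in a conditional form. The charted ID contains an undefined letter whose most natural meaning is the arm. If that is its meaning, one disclosure to someone who sees the IDs exposes 88 of 88 allocations where an uninformative code would expose 1 of 88, and outcomes assessed after that moment are open to bias. The plan's safeguards protect the meaning of the letters but not the grouping.

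The conclusion rests on three assumptions: the letter marks the arm; people who influence or record outcomes see the ID; and one letter is decoded before assessments are complete. The first is likely from the format, the second is plausible but unstated, and the third is made possible by the six-week reveal. The documents do not show that the blind has been or will be broken, and the size of any bias cannot be calculated from them.

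The change is still worth making before the letter's meaning is settled, because it does no harm if the letter turns out to mark a block or batch.

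**What to change.** In the Randomization section:

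1. Replace the number-plus-letter ID with one unique number per bottle (for example 001 to 088) that carries no arm information. The numbers must not run in arm order.
2. Keep the number-to-arm list only with the unblinded holder.
3. Write only that number in the chart.
4. For women already randomised, mask the letter wherever it has been charted.

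If the sponsor prefers to keep the present IDs, the protocol should at least state what the letter means; that is enough only if it does not mark the arm.

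The cost is relabelling bottles and reissuing the code list. Sample size, endpoints and clinical care are unaffected.

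Varying the block size and removing it from the site protocol is optional. Once the codes carry no arm information, the sequence of labels no longer shows how a block will end, so this adds little.

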#### Study Intervention –

10 pills of each IP and placebo will be placed in identical coded containers and stored in a locked area in the clinic. Instructions for IP usage will be provided to subjects for 10 days of usage as 0.4 mg qd by PO route starting 5 days prior to day of surgery and continued for a total 10 days. The research manager will be the only member of the study team who has the research key designating which containers are IP versus placebo.

On postoperative day 0 after recovery from anesthesia, each patient will have their bladder emptied using the indwelling Foley and their bladder will then be retrograde-filled with 300 cc of normal saline and given 30 minutes to void. A postvoid residual volume<150 cc will be considered a success of the voiding trial. If the voiding trial was considered failed, the patient will have a foley catheter reinserted and the patient will be instructed to remove the catheter at home after having a bowel movement. If they are unable to void at home within 4 hours of catheter removal, they will return to the Wake Forest Urology clinic for self-catheter teaching.

# IP Accountability -

IP and placebo bottles will be stored in a locked cabinet on the clinic premises. They will be dispensed to the patient at the time of consent collection and will be brought back by the patient at time of the 1-week postoperative visit. This will be recorded in a study log to keep track of bottles signed in and out. The bottles as well as log will be stored for long-term archiving.

#### Post-Surgery Assessments -

Postoperative day 0 voiding trial result For women who fail initial trial of void, post-operative day when bladder function returned Postoperative exam at 1 and 6 weeks Pelvic examination at 6 weeks Data points to be collected: Post-void residual (PVR), urinalysis (UA), patient level of satisfaction (1-7 – very dissatisfied, moderately dissatisfied, slightly dissatisfied, neutral, slightly satisfied, moderately satisfied, very satisfied)

### Power analysis

For a superiority study, if we assume 5% significance level and 80% power with internal audit rates of POUR of 24.3% for the control group and expecting 2.9% for the tamsulosin group (Chapman), then total sample size would be approximately 74 with n= 37 in each group. Accounting 20% non-compliant and dropout rate, we expect to enroll 88 patients total with 44 in each group. Power calculations done with sealedenvelope.com

Statistical analysis will be performed using IBM SPSS Statistics 24 or similar program.

Baseline and demographic data will be reported using standard descriptive methods. Scores of questionnaires (age, race, BMI, insurance, smoking y/n) and clinical evaluations (menopausal status, vaginal atrophy y/n, estrogen use, type of surgery etc.) will be calculated appropriately. Outcomes will be presented as number with proportion for categorical data and mean and standard deviation (in case of normally distributed data) or median with interquartile range (in case of not normally distributed data). Comparisons within groups will be done for numerical data using either paired t-test (in case of normally distributed data) or Wilcoxon signed rank test (in case of not normally distributed data) and Fisher exact test or Mcnemar for categorical data. Between-group comparisons will be done using either unpaired t-test (in case of normally distributed

data) or Mann-Whitney U test (in case of not normally distributed data) and Chi-square test for categorical data.

	Baseline	Day of surgery	Week 1 post- operative visit	Week 6 postoperative visit
Consent	x			
Dispense IP	x			
Voiding trial		x		
PVR	x	x	х	x
UA	x		х	x
Level of satisfaction with voiding function (1-7)	x	x	x	
Return IP bottle			x	

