# Exclusion criteria:

- 1. Intraoperative complication necessitating prolonged bladder drainage or placement of a vaginal pack x 24 hours (patients would exit study after randomization and will be excluded from the per-protocol analysis)
- 2. Patients whose surgical plan would necessitate a voiding trial on postop day >0
- 3. Less than 21 years of age
- 4. Unable to understand English
- 5. Patients who are scheduled to undergo combined colorectal procedures such as rectopexy, sphincteroplasty
- 6. Patient with known allergy to tamsulosin or sulfa drugs
- 7. Patients with upcoming cataract surgery
- 8. Patient with orthostatic hypotension
- 9. History of postvoid residual (PVR>150) prior to surgery with prolapse reduction
- 10. Patients with hypertension on alpha-blockers
- 11. Single compartment prolapse repair (anterior or posterior repair only)
- 12. Use of mesh for prolapse repair
- 13. High tone pelvic floor dysfunction

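### Enrolling 88 does not cover the stated 20% loss: if all 20% leave the analysis, about 70 women remain, not 74, and 88 covers at most 15.9% loss

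*Combined protocol and SAP*

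**What the plan says.** All the figures are in the Power analysis section of the combined protocol and SAP.

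- Design targets: "if we assume 5% significance level and 80% power". The section does not say whether the test is one- or two-sided.
- Assumed retention rates: "internal audit rates of POUR of 24.3% for the control group", and "expecting 2.9% for the tamsulosin group (Chapman").
- Requirement before losses: "total sample size would be approximately 74 with n= 37 in each group".
- Enrolment: "Accounting 20% non-compliant and dropout rate, we expect to enroll 88 patients total with 44 in each group".

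No inflation formula is given, and the 20% is not divided between non-compliance and dropout.

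Two other sections bear on the point. The Exclusion criteria say of women with certain intraoperative complications that "patients would exit study after randomization and will be excluded from the per-protocol analysis". The Randomization section specifies a "randomly permutated block design (8 subjects per block"). The documents do not name the primary analysis set, do not say whether a non-compliant woman stays in the day-0 comparison, and do not provide for replacing women who leave.

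**The concern.** An allowance for loss is meant to leave the required number after the loss has occurred. A loss rate is normally a share of the women enrolled, so the requirement should be divided by one minus the rate. Multiplying the requirement by one plus the rate gives too few, because the loss then falls on the larger enrolled number.

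This is the trial's only sample-size justification. A reader would take 88 as protecting 80% power against a 20% loss. The margin at the requirement itself is thin, since 37 per arm gives 80.7% by the formula that reproduces it, so a shortfall of even two women per arm takes the trial below its own target.

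**Working it through.** **Inputs** (all from Power analysis): control rate 0.243, tamsulosin rate 0.029, difference 0.214, alpha 0.05, power 0.80, requirement 74 (37 per arm), loss 20%, enrolment 88 (44 per arm). Two-sided testing is inferred, because it is the version that reproduces 37.

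**1. Reproduce the requirement.** Normal approximation for two proportions with unpooled variance:

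n per arm = (1.960 + 0.842)² × [0.243 × 0.757 + 0.029 × 0.971] / 0.214² = 36.35

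Rounded up, this is 37 per arm and 74 in total, an exact match. Unrounded, the total is 2 × 36.35 = 72.7. Other versions do not match: pooled two-sided gives 40 per arm, pooled two-sided with continuity correction 48, and unpooled one-sided 29.

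**2. Reproduce the enrolment.**

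- Requirement × (1 + loss): 74 × 1.2 = 88.8 and 37 × 1.2 = 44.4. Rounded down, these give the stated 88 and 44.
- Requirement / (1 − loss): 74/0.8 = 92.5 and 37/0.8 = 46.25. These do not give 88 or 44.

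**3. Apply the stated loss to the stated enrolment.**

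- Remaining: 88 × 0.8 = 70.4 in total; 44 × 0.8 = 35.2 per arm.
- Shortfall against 74: 74 − 70.4 = 3.6, about 4 women.
- Losses that 88 can absorb: 88 − 74 = 14, and 14/88 = 15.9%. The stated loss is 0.2 × 88 = 17.6 women.
- Against the unrounded 72.7: the shortfall is 72.7 − 70.4 = 2.3, about 2 women, and the tolerated loss is 1 − 72.7/88 = 17.4%.

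**4. Effect on power**, with the formula from step 1:

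power = Φ( 0.214 / √[(0.243 × 0.757 + 0.029 × 0.971)/n] − 1.960 )

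| Evaluable per arm | Power |
|---|---|
| 35 | 78.5% |
| 37 | 80.7% |
| 44 (no loss) | 86.9% |

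The last row assumes that non-compliance does not dilute the effect.

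**The case against.** **The 20% may be meant as an uplift on the requirement.** The plan does not give the base for the percentage, and 74 × 1.2 is within one woman of 88. Rounding down may also have been deliberate, since 88 is exactly 11 blocks of 8. This probably explains where 88 came from, but it does not rescue the sentence. Even 20% of 74 is 14.8, more than the 14 women added, and what is described is a rate of loss, which applies to those enrolled.

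**The loss may not reach the primary comparison.** The primary outcome is a voiding trial on the day of surgery. A woman who misses capsules can still have that trial, and one lost before week 1 or week 6 already has her primary result. This stands, and it is why the shortfall is conditional. But the plan itself inflates for non-compliance and dropout together, and randomization takes place at the pre-operative visit, so loss before the voiding trial is possible. If non-compliant women stay in, more than 70 are analysed but the effect may be diluted, and enlarging the sample for dropout does not deal with that.

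**The requirement is only approximate.** True, but against the unrounded 72.7 the tolerated loss is still below 20%.

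**The power figure depends on the method.** This stands. At 35 per arm the pooled approximation gives 75.4%, against 77.7% at 37. Exact enumeration of the uncorrected chi-square test gives 82.7%, against 84.9% at 37, and Fisher's exact test gives 66.3%, against 70.6% at 37. The plan names the chi-square test for between-group categorical comparisons, and on its uncorrected form 70 women would still exceed 80%. The spread between methods is larger than the loss of about 2 points, so 78% should be quoted only as the result of the formula that reproduces 37. The 15.9% needs no power formula.

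**Conclusion.** The concern holds. An enrolment of 88, a 20% loss from the analysis and 74 evaluable women cannot all be true together, and the sentence should be corrected.

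The practical consequence is small: about 4 women and about 2 points of power under the plan's own rates. With no loss the trial has more power than it needs.

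The conclusion rests on reading the 20% as a share of the women enrolled, and on all of that 20% leaving the analysis in question. The power figures also rest on two-sided testing and unpooled variance, both inferred from the match to 37 per arm. Multiplication by 1.2 as the cause is likewise an inference.

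**What to change.** Replace the enrolment sentence in Power analysis with one of these:

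- Enrolling 88 women allows for up to 15.9% loss while keeping 74 evaluable.
- With 20% loss, about 70 of the 88 women remain, giving about 78% power by the formula used for the 37 per arm.

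The first is safer because it does not depend on the choice of power formula. In either case, add that the statement refers to an analysis that leaves out non-compliant women and dropouts.

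The cost is one sentence. The stated loss allowance falls from 20% to 15.9%, or the stated power from 80% to about 78%. No extra enrolment is needed. If the sponsor would rather keep both the 20% and the 74, the matching enrolment is at least 93: 94 for equal arms, or 96 to complete blocks of 8 (96 × 0.8 = 76.8).

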# Outcomes

#### Primary

To compare rates of POUR following an active voiding trial on postoperative day O between women undergoing multi-compartment native tissue vaginal repair that received preoperative tamsulosin 5 days preoperatively and continued 5 days post operatively versus a group that received placebo

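### The 20% allowance treats non-compliance as lost head-count, so 80% power is not secured for a comparison by randomised arm; it runs from about 62% to 82% depending on points the plan leaves open

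*Combined protocol and SAP*

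**What the plan says.** The Power analysis section is framed by "For a superiority study" and takes "5% significance level and 80% power with internal audit rates of POUR of 24.3% for the control group". For the active arm it is "expecting 2.9% for the tamsulosin group (Chapman"). The result is "total sample size would be approximately 74 with n= 37 in each group". One further sentence covers both non-compliance and dropout: "Accounting 20% non-compliant and dropout rate, we expect to enroll 88 patients total with 44 in each group".

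Three other places bear on this:

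- **Study Intervention** gives the day-0 voiding trial to each patient and sets no condition on pill-taking. The 10-day course starts 5 days before surgery, so part of it falls after the primary outcome.
- **Outcomes, Primary** compares women who "received preoperative tamsulosin 5 days preoperatively and continued 5 days post operatively" with a placebo group. It does not say how women who missed doses are counted.
- **Exclusion criteria**, item 1, contains the only mention of an analysis set, a per-protocol analysis. The exclusion stated there is for an intraoperative complication or prolonged packing, not for missed study drug.

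No section defines an intention-to-treat set, a primary analysis set, or non-compliance itself. IP Accountability logs bottles out and back and describes no pill count.

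**The concern.** Dropout and non-compliance harm a trial in different ways. A woman who drops out before the voiding trial has no primary result, and recruiting another woman makes good the loss. A woman who does not take her capsules but has surgery and the voiding trial does have a primary result. In a comparison by assigned arm she counts as tamsulosin while behaving, at least in part, like a control. The expected difference shrinks, and a larger sample at an undiminished 2.9% does not reflect that.

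The plan puts both into one 20% figure and answers both with head-count. The stated 80% is therefore not a property the design secures for the randomised comparison. If the trial finds no difference, readers will weigh that result against 80% power when the real figure may have been materially lower.

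**Working it through.** **Inputs, all from the Power analysis section.** Control rate p1 = 0.243; tamsulosin rate p2 = 0.029; alpha 0.05; target power 80%; 37 per arm before inflation and 44 after; 20% combined allowance, split not given. Sidedness is not stated. Two-sided reproduces the plan's number; one-sided (pooled formula) gives 31 per arm and does not.

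**Step 1: reproduce the plan.** Two-sided unpooled normal formula:

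n = (1.96 + 0.8416)² × [0.243×0.757 + 0.029×0.971] / (0.243 − 0.029)² = 36.35, so 37 per arm and 74 in total, as stated. Power at 37 per arm is 80.7%.

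Inflation: 37 × 1.2 = 44.4, so 44 per arm and 88 in total, as stated. The rate of 2.9% is carried through unchanged.

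**Step 2: let non-compliers stay in their assigned arm.** Let c be the non-compliant share and d the dropout share, both of women randomised, and let k be the fraction of the drug benefit that non-compliers keep. Both shares are assumed equal in the two arms, and dropout is assumed unrelated to outcome. Non-compliance with placebo changes nothing. Then:

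- women with an outcome per arm: n = 44 × (1 − d)
- non-compliant share of those women: f = c / (1 − d)
- tamsulosin-arm rate: q = 0.029 + f × (1 − k) × 0.214
- power = Φ( (0.243 − q) / √{[0.243×0.757 + q(1 − q)] / n} − 1.96 )

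Worked case, c = 20%, d = 0, k = 0: q = 0.029 + 0.2×0.214 = 0.0718. The difference is 17.1 points instead of 21.4. z = 0.1712 / √(0.2506/44) = 2.27, and power is 62.1%.

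**Step 3: vary the split, with no benefit kept (k = 0).**

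| Non-compliant / dropout | n per arm | f | q | Power |
|---|---|---|---|---|
| 20% / 0% | 44.0 | 20.0% | 7.18% | 62.1% |
| 15% / 5% | 41.8 | 15.8% | 6.28% | 65.7% |
| 10% / 10% | 39.6 | 11.1% | 5.28% | 69.7% |
| 5% / 15% | 37.4 | 5.9% | 4.16% | 74.0% |
| 0% / 20% | 35.2 | 0% | 2.90% | 78.7% |

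**Step 4: vary the benefit kept.**

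| Benefit kept | 20% / 0% | 0% / 20% |
|---|---|---|
| Half | 75.6% | 78.7% |
| Three quarters | 81.6% | 78.7% |

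Intermediate splits lie between the two ends of each row.

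**Step 5: sensitivity to the formula.** The pooled version gives 60.0% for 20%/0% and 75.6% for 0%/20%. Exact power of the uncorrected chi-square test is 63.4% for 20%/0%. With no dilution it is 84.9% at 37 per arm and 82.7% at 35. The choice of formula moves the level by a few points; under each, the fully diluted case stays near 60-63%.

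**Step 6: separate this from the inflation arithmetic.** Dividing by 0.8 instead of multiplying by 1.2 gives 74/0.8 = 92.5, so 93 women. At 46.5 per arm the 20%/0%, no-benefit case still has only 64.5% power. Correcting the head-count does not correct the dilution.

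**The case against.** A reader might infer from Step 3 that 88 women give 62-74% power and not 80%. The documents do not support that as a flat statement, for three reasons.

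- **Analysis set.** No section commits to an as-randomised primary analysis, and the only set named is per-protocol. If all 20% were removed, 35.2 per arm give 78.7% by the plan's formula, close to target. This stands as a limit on the claim. It does not rescue the plan: the stated per-protocol exclusion is not for missed capsules, non-compliance is undefined, and no pill count is described. Removing women after randomisation because of their behaviour would also give up the protection of randomisation.
- **Benefit kept.** Capsules missed after surgery cannot affect a day-0 voiding trial, and missing one or two before surgery is not the same as being untreated. So 62% is a worst case. If non-compliers keep three quarters of the benefit, 20% non-compliance with no dropout gives 81.6%, which meets the target.
- **Split.** The 20% must also cover women who leave after randomisation at the pre-operative visit. If it were all dropout, dilution would play no part.

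It is also tempting to say that the 80% applies to fully compliant women. The plan attributes 2.9% to a cited study and does not say what compliance lay behind it. If that rate was seen under ordinary compliance, it already contains some dilution, and the calculation above would count part of it twice.

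These objections make the size conditional. They do not touch the defect, which is that two different losses are handled by one adjustment that suits only one of them.

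**Conclusion.** The point holds in conditional form. The plan's head-count adjustment is appropriate to dropout only, and non-compliant women can supply the primary outcome, so the stated 80% is not secured for the comparison by randomised arm.

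With 44 randomised per arm and the plan's own rates and formula, power is about 62% to 79% if non-compliers get no benefit, 76% to 79% if they keep half, and 79% to 82% if they keep three quarters. These figures rest on an as-randomised analysis, on the benefit kept by non-compliers, and on the split of the 20%, none of which the documents give. They also take 24.3% and 2.9% as the true rates under full compliance. The plan could be near its target or well short of it; as written, it cannot say which.

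**What to change.** In the Power analysis section:

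1. State that the primary comparison keeps every randomised woman who has a day-0 voiding trial in her assigned arm, whatever her compliance with study drug.
2. Give separate assumed rates for non-compliance and for dropout. Apply the first to the expected tamsulosin rate and the second to the number of women.
3. Replace the single 80% with the conditional range. For example: with 44 randomised per arm, analysed as randomised, power is about 62% if 20% are non-compliant without benefit and none drop out, about 70% at 10% and 10%, about 74% at 5% and 15%, and about 79% if all 20% drop out; if non-compliers keep half the benefit it is about 76-79%, and at three quarters about 79-82%. State the assumptions beside the figures.

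The cost is a few sentences and a stated power that looks less favourable. Enrolment, visits and data collection do not change, and no extra enrolment is proposed.
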